## 12.4 Changes from Version 4.0 to Version 5.0 (Amendment 4)

Section Number (Title)	Change/Rationale
Section 2.1 (Objectives)	A new exploratory objective was added to evaluate early QFT converters (i.e., those that converted at Month 6 or 12) for sustained QFT conversions or late reversions so as to inform the design of subsequent POI studies. Added: To explore trends in QFT-GIT prolonged/sustained conversions and late reversions (i.e., more than 6 months post initial conversion) in early QFT-GIT converters (i.e., among those who converted at Month 6 or Month 12 of follow-up)
Section 2.2 (Design and Endpoints), Section 3.1 (Schedule of Subject Evaluations), Section 3.6.2 (Immunology Laboratory Evaluations), and Appendix A (Detailed Description of Subject Visits)	These sections were updated to include the optional, additional visit for participants who converted to QFT-GIT+ at Month 6 or Month 12.

Section Number (Title)	Change/Rationale
Section 3.2.1 (Recruitment and Informed Consent)	A requirement was added to obtain consent/assent for early QFT converters to participate in the optional, additional follow-up visit described above. Added: Subjects who converted to a positive QFT-GIT at Month 6 or 12 will be approached for an additional QFT-GIT test, blood collection for absolute blood count and RNA, and evaluation for signs/symptoms of TB to be conducted at least 24 months after their initial vaccination. Informed consent will be obtained by the use of a written supplemental consent form approved by the IRB or IEC, and signed and dated by subject or by the subject's parent/legal guardian if subject is less than 18 years of age. Similarly, informed assent will be obtained by the use of a written assent form approved by the IRB or IEC, and signed and dated by the subject if the subject is less than 18 years of age.

## APPENDIX A Detailed Description of Study Visits

### **Screening Visit(s) (All Subjects)**

Written informed consent and assent must be obtained before any screening procedures are performed.

1. Verify study entry eligibility criteria are met
2. Medical history
3. Physical examination
4. Urine collection for urinalysis and (for females)  $\beta$ HCG
5. Vital Signs
6. TB Symptom Screen
7. Blood collection for
  - QuantiFERON®-TB Gold In-Tube
  - HIV-1 (with pre- and post-test counselling)
  - Serum chemistry (AST, ALT, alkaline phosphatase, total bilirubin, creatinine, BUN)
  - Hematology (hemoglobin, hematocrit, white cell count with differential and platelet count)
  - Whole blood for novel IGRA

### **Study Day 0 (All Subjects)**

#### **Pre- injection:**

1. Urine collection (females) for  $\beta$ HCG
2. Obtain pre-immunization vital signs (blood pressure, pulse, axillary temperature)
3. Interval medical history and, if indicated by history, focused physical examination.
4. Verify study entry eligibility criteria are met
5. Randomize
6. Blood collection for
  - PMBC and plasma for correlates of risk protection
  - Whole blood for RNA extraction/absolute blood count
  - Whole blood for novel IGRA
  - PBMC for evaluation of NTM exposure

#### **Safety & Immunogenicity Cohort Only:**

- Whole blood assay
- PMBC for ICS
- Serum for multiplex ELISA

#### **Injection:**

7. Administer either 1) BCG by intradermal injection or 2) AERAS-404 or placebo by intramuscular injection on the left upper arm (deltoid region). Record date and time of injection and which arm was injected.

#### **Post-injection:**

8. Monitor participant for solicited and unsolicited adverse events for at least 30 minutes after injection; record concomitant medications
9. Monitor participant for serious adverse events, adverse events of special interest, and SUSARs for at least 30 minutes after injection; record concomitant medications
10. Obtain 30 $\pm$ 5-minute post-immunization vital signs

11. Complete 30±5-minute post-immunization Study Day 0 study injection site examination (with photograph if there is a visible injection-site abnormality; see Section 5.7 for further details)

***Safety & Immunogenicity Cohort Only:***

12. Distribute diary cards

**Post Study Day 0 Visits (Subjects receiving BCG)**

**Study Day 7 (Subjects receiving BCG)**

*Allowable window for clinic visit is 7±1 days from Day 0*

1. Interval medical history and, if indicated by history, focused physical examination.
2. Monitor participant for solicited and unsolicited adverse events; record concomitant medications
3. Monitor participant for serious adverse events, adverse events of special interest, and SUSARs; record concomitant medications
4. Monitor participant for solicited and unsolicited injection site reaction adverse events; record concomitant medications
5. Complete Study Day 0 injection site examination (with photograph if there is a visible injection-site abnormality; see Section 5.7 for further details)
6. Whole blood collection for RNA extraction/absolute blood count

***Safety & Immunogenicity Cohort only***

7. Urine collection for urinalysis
8. Review diary cards.
9. Blood collection for
  - Serum chemistry (AST, ALT, alkaline phosphatase, total bilirubin, creatinine, BUN)
  - Hematology (hemoglobin, hematocrit, white cell count with differential and platelet count)
  - Serum for multiplex ELISA

**Study Day 28 (Subjects receiving BCG)**

*Allowable window for clinic visit is 28±5 days from Day 0*

1. Interval medical history and, if indicated by history, focused physical examination.
2. Monitor participant for unsolicited adverse events; record concomitant medications
3. Monitor participant for serious adverse events, adverse events of special interest, and SUSARs; record concomitant medications
4. Monitor participant for solicited and unsolicited injection site reaction adverse events; record concomitant medications
5. Complete Study Day 0 study injection site examination (with photograph if there is a visible injection-site abnormality; see Section 5.7 for further details)
6. TB Symptom Screen

**Study Day 70 (Subjects receiving BCG)**

*Allowable window for clinic visit is 70±5 days from Day 0*

1. Interval medical history and, if indicated by history, focused physical examination.
2. Monitor participant for serious adverse events, adverse events of special interest, and SUSARs; record concomitant medications
3. Monitor participant for solicited and unsolicited injection site reaction adverse events; record concomitant medications
4. Complete Study Day 0 study injection site examination (with photograph if there is a visible injection-site abnormality; see Section 5.7 for further details)
5. TB Symptom Screen
6. Blood collection for

- PBMC and plasma for correlates of risk/protection

***Safety & Immunogenicity Cohort only***

7. Blood collection for
  - Whole blood assay
  - PBMC for ICS

**Study Day 84 (Subjects receiving BCG)**

*Allowable window for clinic visit is 84±7 days from Day 0*

1. Interval medical history and, if indicated by history, focused physical examination.
2. Monitor participant for serious adverse events, adverse events of special interest, and SUSARs; record concomitant medications
3. Monitor participant for solicited and unsolicited injection site reaction adverse events; record concomitant medications
4. Complete Study Day 0 study injection site examination (with photograph if there is a visible injection-site abnormality; see Section 5.7 for further details)
5. TB Symptom Screen
6. Blood collection
  - QuantiFERON®-TB Gold In-Tube
  - Whole blood for novel IGRA

**Study Month 6, 12, 18 and 24 (Study Days 168, 336, 504, and 672) (Subjects receiving BCG; to be completed by subjects who did not convert from QFT-GIT(-) to QFT-GIT(+) at the previous visit)**

*Allowable window for clinic visit is 6, 12, 18, or 24 months (168, 336, 504, 672 days) ±14 days from Day 0*

1. Interval medical history and, if indicated by history, focused physical examination.
2. Monitor participant for serious adverse events, adverse events of special interest, and SUSARs; record concomitant medications
3. TB Symptom Screen
4. Blood collection
  - QuantiFERON®-TB Gold In-Tube
  - Whole blood for novel IGRA
  - [Study Months 6 and 12 only]PBMC and plasma for correlates of risk protection
  - Whole blood for RNA extraction/absolute blood count

**Study Month 6 (Study Day 168) (Subjects receiving BCG; to be completed by subjects who converted from QFT-GIT(-) to QFT-GIT(+) at Study Day 84)**

*Allowable window for clinic visit is 6 months (168 days) ±14 days from Day 0*

1. Monitor participant for serious adverse events, adverse events of special interest, and SUSARs; record concomitant medications
2. TB symptom screen

**84 and 168 Days after conversion from QFT-GIT(-) to QFT-GIT(+) at Months 6-24 (Subjects receiving BCG; to be completed by subjects who converted from QFT-GIT(-) to QFT-GIT(+) at Month 6-24 visits)**

*Allowable window for clinic visit is 84 or 168 days ±14 days after conversion*

1. Monitor participant for serious adverse events, adverse events of special interest, and SUSARs; record concomitant medications
2. TB symptom screen
3. Blood collection
  - QuantiFERON®-TB Gold In-Tube

- Whole blood collection for RNA extraction/absolute blood count

**Final visit for subjects who converted from QFT-GIT(-) to QFT-GIT(+) at Month 6 or 12 (Subjects receiving BCG)**

Written informed consent and assent must be obtained for additional follow-up before any extended follow-up procedures are performed.

*Allowable window for clinic visit is at least 24 months after initial vaccination but before the end of the study*

1. TB symptom screen
2. Record TB treatment, if applicable
3. Blood collection
  - QuantiFERON®-TB Gold In-Tube
  - Whole blood for RNA extraction/absolute blood count

**Post Study Day 0 Visits (Subjects receiving AERAS-404 or placebo)**

**Study Day 3 (Subjects receiving AERAS-404 or placebo)**

*Allowable window for clinic visit is 3±1 days from Day 0*

1. Interval medical history and, if indicated by history, focused physical examination.
2. Monitor participant for solicited and unsolicited adverse events; record concomitant medications
3. Monitor participant for serious adverse events, adverse events of special interest, and SUSARs; record concomitant medications
4. Monitor participant for solicited injection site reaction adverse events at Study Day 0 injection site; record concomitant medications
5. Complete Study Day 0 injection site examination (with photograph if there is a visible injection-site abnormality; see Section 5.7 for further details)
6. Whole blood collection for RNA extraction/absolute blood count

***Safety & Immunogenicity Cohort only***

7. Blood collection for
  - Serum for multiplex ELISA

**Study Day 7 (Subjects receiving AERAS-404 or placebo)**

*Allowable window for clinic visit is 7±1 days from Day 0*

1. Interval medical history and, if indicated by history, focused physical examination.
2. Monitor participant for solicited and unsolicited adverse events; record concomitant medications
3. Monitor participant for serious adverse events, adverse events of special interest, and SUSARs; record concomitant medications
4. Monitor participant for solicited injection site reaction adverse events at Study Day 0 injection site; record concomitant medications
5. Complete Study Day 0 injection site examination (with photograph if there is a visible injection-site abnormality; see Section 5.7 for further details)

***Safety & Immunogenicity Cohort only***

6. Urine Collection for urinalysis
7. Review diary cards.
8. Blood collection for
  - Serum chemistry (AST, ALT, alkaline phosphatase, total bilirubin, creatinine, BUN)
  - Hematology (hemoglobin, hematocrit, white cell count with differential and platelet count)

**Study Day 28 (Subjects receiving AERAS-404 or placebo)**

*Allowable window for clinic visit is 28±5 days from Day 0*

1. Interval medical history and, if indicated by history, focused physical examination.

2. Monitor participant for unsolicited adverse events; record concomitant medications
3. Monitor participant for serious adverse events, adverse events of special interest, and SUSARs; record concomitant medications
4. Monitor participant for solicited injection site reaction adverse events at Study Day 0 injection site; record concomitant medications
5. Complete Study Day 0 injection site examination (with photograph if there is a visible injection-site abnormality; see Section 5.7 for further details)
6. TB Symptom Screen

**Study Day 56 (Subjects receiving AERAS-404 or placebo)**

*Allowable window for clinic visit is 56-2/56+14 days from day 0*

**Pre- injection:**

1. Urine collection (females) for  $\beta$ HCG
2. Obtain pre-immunization vital signs (blood pressure, pulse, axillary temperature)
3. Interval medical history and, if indicated by history, focused physical examination.
4. Verify study entry eligibility criteria are met

**Injection:**

5. Administer AERAS-404 or placebo by intramuscular injection on the right upper arm (deltoid region). Record date and time of injection and which arm was injected.

**Post-injection:**

6. Monitor participant for solicited and unsolicited adverse events for at least 30 minutes after injection; record concomitant medications
7. Monitor participant for serious adverse events, adverse events of special interest, and SUSARs for at least 30 minutes after injection; record concomitant medications
8. Monitor participant for solicited injection site reaction adverse events at Study Day 56 injection site; record concomitant medications
9. Obtain 30 $\pm$ 5-minute post-immunization vital signs
10. Complete 30 $\pm$ 5-minute post-immunization Study Day 56 study injection site examination (with photograph if there is a visible injection-site abnormality; see Section 5.7 for further details)
11. TB symptom screen

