### 3.2.4 Exclusion Criteria

**Subjects must have none of the following at the time of randomization:**

1. Acute illness on Study Day 0
2. Axillary temperature  $\geq 37.5^{\circ}\text{C}$  on Study Day 0
3. Abnormal laboratory values from the most recent blood collected prior to randomization as follows:
  - Laboratory evidence of hematologic disease (white blood cell count  $< 3000/\text{mm}^3$  or  $> 11,500/\text{mm}^3$ ; hemoglobin  $< 0.9$  times the lower limit of normal of the testing laboratory, by age and gender; absolute neutrophil count  $< 1300/\text{mm}^3$ ; absolute lymphocyte count  $< 1000/\text{mm}^3$ )
  - ALT, AST, alkaline phosphatase, total bilirubin, creatinine, blood urea nitrogen (BUN)  $> 1.25$  times the upper limit of normal of the testing laboratory
4. Greater than Grade 1 on the Toxicity Scale urinalysis result (with the exception of hematuria in a menstruating female), or urinalysis abnormality judged clinically significant by the investigator
5. History or evidence of any clinically significant systemic disease, or any acute or chronic illness that might affect the safety, immunogenicity, or efficacy of study vaccine in the opinion of the investigator
6. History of treatment for active TB disease or latent *Mtb* infection
7. History or evidence, including chest X-ray, of active TB disease
8. Shared residence with an individual receiving anti-TB treatment, or known to have incompletely treated culture or smear positive TB, at screening
9. History of autoimmune disease or immunosuppression
10. Used immunosuppressive medication within 42 days before Study Day 0 (inhaled and topical corticosteroids are permitted)
11. Received immunoglobulin or blood products within 42 days before Study Day 0

12. Received any investigational drug therapy or investigational vaccine within 182 days before Study Day 0, or planned participation in any other clinical trial during the study period
13. Received investigational TB vaccine, other than BCG, at any time prior to Study Day 0
14. Planned administration/administration of a licensed vaccine in the period starting 28 days before and ending 28 days after each dose of study vaccine
15. History or laboratory evidence of any past or present possible immunodeficiency state including, but not limited to, any laboratory indication of HIV-1 infection
16. History of allergic disease or reactions, including eczema, likely to be exacerbated by any component of the study vaccine

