### 3.2.5 Screening Clinical Assessments and Laboratory Tests

Unless noted otherwise, the window period within which all screening evaluations must be completed, and the results reviewed by the investigator to confirm eligibility of subjects, is 21 days prior to and including Study Day 0.

Subjects will provide a detailed medical history and undergo a physical examination. Demographic characteristics (date of birth, gender, and race/ethnicity) will also be collected. A dipstick urinalysis, urine pregnancy test (all females), QFT-GIT test, and an HIV rapid test with repeat confirmation of all positive tests, will be performed. Any new abnormal findings will be discussed with the subject and referral will be made for follow-up care if necessary.

Screening laboratory tests (including serum chemistry, complete blood count, differential blood count, platelets, and hepatic enzymes) will be performed during the screening process. Results from these laboratory tests will serve as study-entry baseline values. Abnormal results and findings that make the subject ineligible will be discussed with the subject and the subject will be referred for follow-up care with their healthcare provider if necessary. All screening laboratory specimens will be processed according to laboratory SOPs available from the clinical laboratory(ies) designated for the study. Information about the laboratory(ies), including any instructions for performing and interpreting specific tests, will be maintained in the investigator's study files.

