### 6.1 Rules for Discontinuing Study Injections in an Individual Participant

Administration of additional study injections will be discontinued for an individual participant if he/she has any of the following:

- An objective clinical or laboratory parameter change which meets Grade 3 or Grade 4 severity, as defined in the protocol toxicity table, AND is judged to be possibly, probably, or definitely related to study injection\*
- Adverse event thought to be an allergic reaction to the study injection, including anaphylaxis or bronchospasm
- Any extensive rash (>40% body surface) on the thorax, abdomen, or limbs, including but not limited to urticaria, generalized petechiae, or erythema multiforme judged to be possibly, probably, or definitely related to study injection
- Development of active TB
- Development of autoimmune disease or immunosuppression, or an adverse event of special interest
- Receipt of investigational drug therapy or investigational vaccine (other than study injections received as part of this study)
- Any event that in the opinion of the principal investigator precludes administration of any further study injections
- Pregnancy

\*Excluding local injection site redness, induration, or ulceration that follow the normal expected course of BCG vaccination.

Subjects who are withdrawn from vaccination will be followed for a minimum of 6 months after the last study vaccination for safety.

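### The Day 56 TB symptom screen is listed after the second AERAS-404/placebo injection, so it cannot inform the decision to give that dose

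*Protocol*

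**What the plan says.** Appendix A, Study Day 56 (subjects receiving AERAS-404 or placebo), sets the order by its own headings:

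- Pre-injection, items 1 to 4: urine pregnancy test for females; vital signs including axillary temperature; interval history, with a focused examination if the history calls for it; and, last, "Verify study entry eligibility criteria are met".
- Injection, item 5: the second dose.
- Post-injection, items 6 to 11: adverse event monitoring, vital signs, injection site check and, at the end, "11. TB symptom screen". Item 12, diary cards, applies only to the Safety & Immunogenicity Cohort.

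Table 3-2 marks the screen at Day 56 but gives no order within the visit.

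The second dose is conditional. Section 3.5 withholds it from anyone who has met a Section 6.1 criterion and defers it for short-term illness or significant active infection. The Section 6.1 criteria include "Development of active TB" and "Any event that in the opinion of the principal investigator precludes administration of any further study injections". The entry criteria re-checked at item 4 include exclusion 7, "History or evidence, including chest X-ray, of active TB disease", and exclusion 5, which begins "History or evidence of any clinically significant systemic disease, or any acute or chronic illness that might affect the safety".

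**The concern.** The protocol treats TB symptom screening as a safety priority (Section 3.6.1) and makes active TB a reason to stop injections. Day 56 is the only dosing visit with a scheduled TB screen, yet the answers arrive after the dose has been given. Nothing in the screen depends on the injection: Section 3.6.1 describes symptoms lasting more than two weeks. The documents give no reason for asking afterwards.

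At stake is a participant whose TB-compatible symptoms are missed by the interval history and the eligibility check. That participant would receive dose 2 and only then be asked the specific questions already scheduled for the same visit. The concern is safety alone. The QFT-GIT endpoints, error rates and sample size are not affected.

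**Working it through.** **Order.** The injection is item 5 and the screen is item 11. The headings make this a sequence, not a neutral list. Table 3-2, Section 3.5, Section 3.6.1 and Section 6.1 do not place the screen earlier. The plan gives no figure on this point to reproduce, so what follows sizes the gap.

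**Age of the last structured screen before each dose.**

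- Dose 1: the window for screening evaluations "is 21 days prior to and including Study Day 0", so the screening-visit TB screen is at most 21 days old.
- Dose 2: the last earlier screen is at the Day 28 visit (window ±5, so Day 23 to 33), and the dose window is Day 54 to 70. The nominal age is 56 − 28 = 28 days; the range is 54 − 33 = 21 to 70 − 23 = 47 days.

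**Which symptoms fall in the gap.** Symptoms present at Day 28 can be caught there, either by the screen or by unsolicited adverse event collection, which has no two-week minimum (Table 3-4; Appendix A, Study Day 28). What remains is onset after Day 28 but at least 14 days before Day 56:

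(56 − 14) − 28 = 14 days.

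**Expected cases.** Inputs: 330 participants per arm, so 660 planned for a Day 56 injection (Table 3-2); TB incidence of 220 per 100,000 person-years in QFT-GIT negative adolescents (Section 1.1); or the protocol's planning figure of 0.2% (Section 2.2).

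- Person-time: 660 × 14 / 365.25 = 25.3 person-years.
- At 0.0022 per year: 25.3 × 0.0022 = 0.056 cases.
- At 0.0020 per year: 25.3 × 0.0020 = 0.051 cases.
- AERAS-404 arm only: 330 × 14 / 365.25 × 0.0022 = 0.028 cases.

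If Day 28 adverse event reporting is ignored, the Day 28 screen catches only onset by Day 14. The gap becomes (56 − 14) − (28 − 14) = 28 days, and the count is 660 × 28 / 365.25 × 0.0022 = 0.111 at nominal visit days.

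**The case against.** The strongest reply is that the screen has another job. Section 3.6.1 presents it as a route to early diagnosis, sputum testing and referral, and no text makes it a gate for dosing. Dose 1 has no same-day screen either. The real gate comes before the injection and is in one respect broader: Section 3.5 calls for deferral for acute febrile or respiratory illness with no two-week minimum, and temperature, history and the eligibility re-check are all done first. Participants are also reminded at each visit to report changes in health (Section 3.6.4), and adverse events are followed until resolution (Section 5.3). A positive screen leads to sputum tests, so it would rarely establish active TB that day. AERAS-404 is a protein with adjuvant, and the documents show no harm from one dose in unrecognised early TB.

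Much of this stands, and it is why the point is minor. It does not remove the point. At the Screening visit in Appendix A the same screen sits alongside eligibility verification, so it does serve as an input to dosing there. Section 3.5 states when to defer but is not a step that asks the TB questions. The interval history is unstructured, and the examination depends on what that history brings out. A positive screen need not prove TB to be useful: it could support deferral within the existing window.

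One practical limit also stands. The SAP describes the conduct of the trial in the past tense and the primary analysis as completed (SAP Sections 3.1 and 4.2). For this trial the change may mainly correct the procedure of record. It remains useful for any further dosing or any later protocol that reuses the visit list.

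**Conclusion.** The point holds as a minor matter of sequence. The structured Day 56 TB screen, done as listed, cannot inform the second dose. This is true of that one screen, not of all TB assessment before the dose.

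The expected number of affected participants is about 0.05 to 0.06 TB cases among 660, about 0.03 of them in the AERAS-404 arm, and about 0.11 overall if Day 28 adverse event reporting is given no credit. These figures assume nominal visit days, all 660 receiving dose 2, a constant incidence, qualifying symptoms in every TB case, and a Day 56 history and eligibility check that miss every one. The last two assumptions overstate the residual, so the true gain from reordering is very small.

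**What to change.** In Appendix A, Study Day 56 (AERAS-404 or placebo), move the TB symptom screen from post-injection item 11 into the pre-injection list, directly before the eligibility check, and renumber. Add no new deferral rule: the investigator decides under Sections 3.5 and 6.1 and the existing re-verification.

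The edit moves one line and adds no procedure, visit or blood draw. The downside is an occasional deferral within the Day 54 to 70 window, which can push the Day 84 QFT-GIT visit late. Appendix A sets that visit at 28 ± 5 days from Day 56, read here as the second dose; SAP Appendix 8 sets it at 84 ± 7 days from Day 0, that is, Day 77 to 91.

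- The nominal visit stays inside if dose day + 28 ≤ 91, so a dose by Day 63.
- The earliest allowed visit stays inside if dose day + 23 ≤ 91, so a dose by Day 68.
- A dose on Day 69 or 70 puts even the earliest visit on Day 92 or 93, outside the window.

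A dose lost altogether removes the participant from the Per Protocol set (SAP Section 5.5). The documents do not allow the number of such deferrals to be estimated.
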